percentage of days abstinent (PDA) and percentage of days of heavy drinking (PDH). We believe that this is a conservative estimate given the method in which the planned HLM handles missing data. In a two-tailed test adjusted for conducting correlated tests of drinking behavior over time ($\alpha = .05/2 = .025$), the baseline dependent measure entered as a fixed covariate and 1 *df* for the between-group term, we estimate that we will have .703 power to reject the null hypothesis of no difference between TAU and TAU + B-FIT with 51 participants and an effect size of .20 ($d = .25$ to achieve power of .80).

Statistical analyses. An extensive set of analyses is proposed that includes the assessment of treatment fidelity, document CFM and patient satisfaction with the B-FIT intervention, and examine outcomes in general, mechanisms of change, and potential moderators of treatment response. Initial attention will be directed to investigating overall and between-group attrition rates and distributions of key measures prior to conducting primary analyses. Although quantitative support will be provided in the achievement of all study Aims, the described statistical analyses will focus on the stated objectives in study Aim 2a, 2c, and 2d, which are central to the proposed model (Figure 1).

Aim 2a. Obtain estimates of the relative impact of B-FIT on patient treatment adherence, drinking outcomes, family functioning, and functioning of the CFM. Treatment adherence will be defined as the total number of TAU sessions attended between randomization and the 4-month follow-up interview (measured by the TSR and Form-90). Two primary alcohol use measures will be considered and aggregated into four monthly values: proportion abstinent days from alcohol (PDA: days abstinent/ 30 days) and percentage of days of heavy drinking (PDH). Family functioning will be assessed using the Cohesion and Conflict subscales of the Family Environment scale, and the Family Communication scale total score. CFM functioning will be defined as total scores on the Beck Depression Inventory (BDI) and Beck Anxiety Inventory (BAI).

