Generalized linear models (GLM) will assess the relative benefit of the B-FIT intervention to TAU alone on treatment adherence, family, and CFM functioning. Parameter estimates will be derived using maximum likelihood with robust estimators. In the treatment adherence GLM, two covariates are planned: number of TAU sessions attended *prior* to randomization and baseline PDA. The dependent measure will be the total number of TAU sessions attended from randomization to the 4-month follow-up and treatment assignment will be entered as a between-subject factor. A two-tailed test will be done with Type I error set at $\alpha = .05$. Four GLMs will be used to assess the relative benefit of B-FIT on family functioning; two using the patient 4-month report of family Cohesion and Conflict and two based upon CFM 4-month report of family Cohesion and Conflict. Baseline values of the two scales will be used as covariates. Treatment group will be entered into the model as a between-subject factor and Type I error will be adjusted to $\alpha = .05/2 = .025$ in the two-tailed tests. The relative benefit of B-FIT on CFM functioning will be determined using two GLMs. The first GLM will use 4-month BDI scores as the dependent measure and baseline values of the BDI will be entered as a covariate. Baseline values of PDA for the CFM also will be entered as a covariate to negate any influence of drinking on self-reported depression. Treatment assignment will be entered as a between-subject factor. A second GLM following the same strategy then will use the 4-month BAI score as the dependent measure. These tests of CFM functioning will be adjusted by $\alpha = .05/2 = .025$ to control for inflated Type I error.

The relative benefit of adding the B-FIT sessions to TAU on drinking over four months will be determined using two longitudinal hierarchical linear models, one for PDA and a second for PDH (Raudenbush & Bryk, 2002). Modeling of change in alcohol use will be restricted to the linear effect given the limited number of time points. The random intercept in the unconditional models will be examined first, followed by fitting the conditional models, which will introduce baseline value of the respective drinking measure (PDA or PDH) as a fixed covariate and the random linear time term. Treatment group will then be entered in level two of the model and will be tested via the *t*-statistic.

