Cross-level interactions will be tested via the *t*-statistic to identify potential time by group interactions in changes in alcohol use. Type I error will be adjusted to $\alpha = .05/2 = .025$ to account for the correlation between PDA and PDH.

Aim 2c. This aim will investigate whether the relative benefit of B-FIT occurred for the presumed reasons. As such, this aim will focus only on participants assigned to the B-FIT group ($n = 40$ at baseline). Tests of mediation will use a product-of-coefficients approach with a bootstrapping procedure (Hayes, 2009). This choice provides the most powerful test of mediation with smaller samples and does not assume normality in the distribution of ($a'b'$) product terms (Preacher and Hayes, 2008; Hayes, 2009). Three active ingredients of B-FIT will be investigated separately: (1) teaching skills to reinforce change, (2) teaching skills to increase positive exchanges, and (3) teaching skills to improve communication, all of which are measured within treatment by the modified C-TIRS. Baseline values of mediators will be entered into all planned analyses as covariates. Overall, we will conduct six mediational tests. First, we will conduct 3 mediational tests to evaluate our prediction that teaching skills to reinforce change will increase 4-month abstinence (PDA) by mobilizing three mediators during the treatment phase of the study (TAU treatment adherence, commitment to abstinence, and perceived family support). The fourth test will examine if teaching skills to reinforce change increases family satisfaction (month 4) through enhanced impressions of perceived family support (within treatment). Our fifth test will examine if teaching skills to enhance positive family exchanges produces increased family satisfaction (month 4) by increasing positive shared time (within treatment). Finally, we will assess if teaching skills to improve communication increases 4-month family relationship satisfaction by mobilizing more positive partner communications within treatment. No adjustment for inflated Type I error is planned for these six tests.

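### The .025 level for PDA and PDH is a valid but conservative Bonferroni split that does not use their correlation; Holm within each two-outcome pair is a free improvement.

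*Combined protocol and SAP*

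**What the plan says.** All references are to STUDY DATA, II. Data Analysis/Statistical Considerations.

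- **Aim 2a, drinking outcomes.** The plan fits "two longitudinal hierarchical linear models, one for PDA and a second for PDH". Each model tests the treatment-group term. Each also tests cross-level terms "to identify potential time by group interactions in changes in alcohol use". The next sentence sets Type I error at .05/2 = .025 "to account for the correlation between PDA and PDH".
- **Statistical power.** The power figure uses the same level, for a two-tailed test "adjusted for conducting correlated tests of drinking behavior over time". With 34 B-FIT and 17 treatment-as-usual (TAU) patients and an effect size of .20, "we estimate that we will have .703 power to reject the null hypothesis of no difference between TAU and TAU + B-FIT".
- **Aim 2a, family member functioning.** The Beck Depression Inventory (BDI) and Beck Anxiety Inventory (BAI) models use the same division: "These tests of CFM functioning will be adjusted by" .05/2 = .025. The reason given there is control of Type I error, which is the correct one.

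The plan gives no value for the PDA-PDH correlation and specifies no step-down or correlation-based procedure.

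**The concern.** The stated reason does not match the method. The level would be .025 whether PDA and PDH were independent or nearly identical, so nothing has been done about their correlation. A reader who takes the sentence at face value will think the dependence has been used.

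The practical cost is that the second drinking outcome is held to .025 even after the first has been declared. A standard alternative avoids this at the same error bound. With 51 analysed patients and a stated power of .703, there is little reason to give that up.

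**Working it through.** **Inputs from the plan.** Two outcomes; two-sided .025 each; stated power .703; 34 versus 17 analysed; effect size .20, with .25 said to give .80.

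**Assumptions of this check.** The two test statistics are bivariate normal. Their correlation, after aligning signs so that benefit is positive on both, runs from 0 to .9. The plan gives no value.

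**1. Can .703 be reproduced?** Not clearly.
- .20 read as d: λ = .20² × (34 × 17/51) = .453, and the F test at .025 has power .058. With .25 it is about .08.
- .20 read as Cohen's f, one measurement: λ = 51 × .20² = 2.04, power .198.
- .20 read as f with four uncorrelated monthly values: λ = 4 × 2.04 = 8.16, power .705. This is close, but .25 then gives .89, not .80. A within-person correlation of .5 gives λ = 8.16/2.5 = 3.26 and power .315.

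The .703 is therefore taken as the plan's claim and is not confirmed here.

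**2. Error rate of the fixed split, both nulls true.** At correlation 0 it is 1 − .975² = .0494. It falls to .047, .043, .040 and .036 at correlation .5, .7, .8 and .9. A level that did use the correlation would be .0270, .0293 and .0350 per test at .5, .7 and .9.

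**3. Holm against the fixed split.** Critical values are z(.9875) = 2.241 and z(.975) = 1.960. The implied non-centrality is 2.241 + z(.703) = 2.241 + 0.533 = 2.774. Power at .05 is then Φ(2.774 − 1.960) = .792, which is the ceiling.

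Holm's power for outcome 1 is P(|Z1| > 2.241) + P(1.960 < |Z1| ≤ 2.241 and |Z2| > 2.241).

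At correlation 0 this is .703 + (.792 − .703) × .703 = .766. Power for both is .703² = .494 under the fixed split. Under Holm it is .792² − (.792 − .703)² = .620 (unrounded values carried). The other rows come from simulation with 4 million draws.

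| Correlation | Per outcome: fixed → Holm | Both: fixed → Holm | At least one (either method) |
|---|---|---|---|
| 0 | .703 → .766 | .49 → .62 | .91 |
| .5 | .703 → .756 | .56 → .67 | .85 |
| .7 | .703 → .751 | .59 → .69 | .81 |
| .9 | .703 → .742 | .64 → .72 | .77 |

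**4. When the conditions change** (correlation 0 to .9).
- One outcome with half the non-centrality: the weaker outcome gains about 6 to 9 points (from .197 to .258–.284), the stronger 0 to 2.
- Only one outcome has an effect: that outcome gains 0 to 0.2 points. Holm's false-rejection rate on the null outcome is .038 to .042, still below .05.
- .20 a literal d (power about .06): each outcome gains 0.3 to 1.1 points.

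**5. Error under Holm, both nulls true.** Holm's first rejection needs the smaller p-value to pass .025, exactly as in the fixed split. The familywise rates in step 2 therefore apply unchanged.

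**The case against.** **The plan contains no statistical error.** This stands. The split is valid, and the disputed clause may mean only that two related outcomes are treated as one family. A reader might infer that the mistaken reason makes the tests invalid or inflates the error over the two outcomes. The error rates above show the opposite.

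**Holm ignores the correlation too.** This also stands. Holm recovers power, but it does not make the sentence about correlation true. That wording needs its own correction.

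**The gain is conditional.** A reader might infer a flat loss of 4 to 6 points, or a lower chance of finding any drinking effect. The documents support neither. They do not say that the effects on PDA and PDH are equal, they give no correlation, and .703 does not follow clearly from their inputs. The chance of declaring at least one outcome is the same under both methods.

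**The family may be four tests, not two.** This is the strongest objection. The .025 sentence directly follows the group-by-time tests. Four tests at .025 have an error bound of .10 (1 − .975⁴ = .096 if independent). With null, independent interaction terms, Holm over all four gives per-outcome power of about .63, below .703. If Holm is applied to the group terms and the interactions stay at .025, with one real group effect, the error over all four rises from .060–.073 to .072–.090. So the advantage holds only for a stated two-test family, and that family has to be written down.

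**The trial is developmental.** Holm changes no effect estimate, and much of Aim 2a is estimation. But the power section also puts substantial weight on inferential testing, so the tests should be well specified.

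**Conclusion.** The point holds as a free improvement, not as a validity problem. The .025 level is a conservative Bonferroni split and does not account for the correlation. For the PDA and PDH group terms, Holm never rejects less and keeps the .05 bound under any dependence.

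The gain is about 4 to 6 points per outcome and 8 to 13 points for both. It rests on three things: both outcomes having .703 power at .025, an assumed correlation of 0 to .9, and a family limited to the two group terms. Where effects are unequal, most of the gain goes to the weaker outcome; where only one effect is real, it is close to nil. For BDI and BAI the same dominance applies, but the plan states no power for them, so no gain can be quantified.

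**What to change.** 1. For the PDA and PDH treatment-group terms, test the smaller p-value at .025; if it is rejected, test the other at .05.
2. Do the same for the BDI and BAI models.
3. Replace the wording about correlation, in Aim 2a and in the power paragraph, with a statement that the procedure controls Type I error over the two outcomes.
4. Describe the stated power as that of a test at .025, which is a lower bound per outcome under Holm.
5. State that the two-test drinking family is the group terms only and that the group-by-time tests are outside it, as secondary or exploratory. The .05 bound does not cover all four drinking tests under either method.

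**Cost.** A few sentences in the analysis section; no new data or patients. The one downside is that confidence intervals matching Holm are less simple than Bonferroni intervals. Aim 2a specifies no intervals at present, so this matters only if they are added.

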The proposed study takes this next step. Specifically, the treatment to be developed and tested in this grant, "B-FIT" (Brief Family-Involved Treatment), is designed as an add-on to community-based substance abuse treatment-as-usual (TAU). B-FIT uses family involvement to enhance patient treatment adherence and outcomes by improving family functioning and increasing family-provided incentives for treatment adherence and abstinence. Study aims are carefully sequenced to develop the B-FIT treatment and judge its merits.

Figure 1. Proposed relations among B-FIT active ingredients, mediators, and outcomes

OBJECTIVES/AIMS/HYPOTHESES

The overall study has three specific aims:

Aim 1. To modify our existing ABCT model to make it (a) appropriate for any concerned family member, (b) shorter, (c) focused on key mechanisms of change identified in prior research, (d) appropriate for use as part of an on-going alcohol treatment program, and (e) more efficacious by incorporating behavioral contracting procedures (O'Farrell & Fals-Stewart, 2000; Smith & Meyers, 2004).

Aim 2. To conduct a small-scale clinical trial of B-FIT to: **Aim 2a.** Obtain preliminary effect-size estimates of the impact of B-FIT on (a) patient treatment adherence; (b) drinking outcomes; (c) family functioning; and (d) functioning of the concerned family member. **Aim 2b.** Obtain estimates of the disseminability of the protocol by assessing: (a) clinicians' ability to learn and implement the

intervention; (b) clinician evaluations of the ease of protocol implementation; (c) patient and family member feedback about B-FIT; and (d) the proportion of patients and concerned family members willing to participate in the intervention. **Aim 2c.** Develop and conduct a preliminary test of a methodology to study the active ingredients in the B-FIT treatment and purported mechanisms by which it works. **Aim 2d.** Test major moderators of the treatment effect: (a) demographic variables and severity of AUD; (b) individual psychological variables; and (c) familial distress/support.

Aim 3. Finalize materials for a larger-scale RCT, including: (a) treatment manual; (b) patient and family manuals; (c) clinician training materials; (d) a treatment integrity rating system; (e) all measures.

The focus of this IRB application is the pilot study and randomized clinical trial. We were previously approved for the focus group portion of the study in IRB application 01815.

STUDY DESIGN AND PROCEDURES

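### Aim 2c asks why B-FIT did better than TAU but models only the B-FIT arm, so its mediation tests show within-arm associations and cannot explain the difference between arms

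*Combined protocol and SAP*

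**What the plan says.** In STUDY DATA, II. Data Analysis/Statistical Considerations, Aim 2c opens with its question: "This aim will investigate whether the relative benefit of B-FIT occurred for the presumed reasons". The next sentence sets the population: "As such, this aim will focus only on participants assigned to the B-FIT group", given as 40 at baseline. Under Aim 2a the same section uses relative benefit for B-FIT added to TAU against TAU alone.

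The method is stated as follows: "Tests of mediation will use a product-of-coefficients approach with a bootstrapping procedure". The predictors are three B-FIT ingredients, "all of which are measured within treatment by the modified C-TIRS". Three tests take 4-month PDA as outcome and suppose that teaching reinforcement skills works by "mobilizing three mediators during the treatment phase of the study (TAU treatment adherence, commitment to abstinence, and perceived family support". The other three take 4-month family satisfaction as outcome. Baseline values of the mediators are covariates, and the six tests are not adjusted for multiplicity.

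OBJECTIVES/AIMS/HYPOTHESES words Aim 2c more modestly: "Develop and conduct a preliminary test of a methodology to study the active ingredients in the B-FIT treatment and purported mechanisms by which it works".

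One of the mediators, treatment adherence, is defined under Aim 2a as the "total number of TAU sessions attended between randomization and the 4-month follow-up interview". It is compared between arms there, with assignment as a factor.

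**The concern.** An advantage of B-FIT over TAU is a contrast between arms. To say that a mediator explains it, one must show that assignment moved the mediator and that the mediator is linked to the outcome. Aim 2c drops the TAU arm, so the first step is missing. What remains is the relation between how much of an ingredient was delivered and the mediator, among patients who all received B-FIT. Delivery was not randomized within that arm.

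The plan itself suggests how such a relation could arise without the ingredient being its cause. The recovery contract is introduced only in session 2 (TAU + B-FIT), and about 20% of dyads are expected not to finish three sessions (Participant Enrollment). A less engaged dyad may receive less reinforcement teaching, attend fewer TAU sessions and have a lower PDA.

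At stake is the sentence the trial would publish. A significant product of coefficients could be presented as the reason B-FIT outperformed TAU even if B-FIT left the mediator where TAU left it. The statistical section calls Aim 2c central to the proposed model, and Aim 3 prepares a larger trial, so a wrong attribution could carry forward.

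**Working it through.** **The plan's own figures.** The Statistical power paragraph gives 15% attrition and 34 B-FIT plus 17 TAU patients at follow-up. Working back, 34/0.85 = 40, 17/0.85 = 20 and 51/0.85 = 60. The 40 stated in Aim 2c is reproduced. Aim 2c therefore uses 34 of 51 followed patients and leaves out 17 (17/51 = 33%).

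**Which paths are planned.** Counting the six tests:
- Reinforcement teaching to adherence, commitment and family support, each then to PDA: 3 a-paths, 3 b-paths.
- Reinforcement teaching to family support, then to satisfaction: the a-path is already counted; 1 new b-path.
- Positive-exchange teaching to shared time, then to satisfaction: 1 a, 1 b.
- Communication teaching to partner communication, then to satisfaction: 1 a, 1 b.

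The total is 5 a-paths and 6 b-paths, as the plan states in its homogeneity check. None starts from assignment. Both post hoc strategies reuse these same models. Assignment appears only in Aims 2a and 2d, and neither tests mediation.

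**Why one arm is not enough.** Let Z be assignment, X the ingredient rating, M the mediator and Y the outcome. The part of the arm difference carried by M is a_Z × b, where a_Z is the mean of M under B-FIT minus its mean under TAU. With Z = 1 for everyone, a_Z cannot be estimated. The planned product is a_X × b, where a_X is the slope of M on X within B-FIT. Neither a_X nor a_Z determines the other.

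**Illustration (assumed effects, none from the documents).** Percentile bootstrap of the product, 34 versus 17 patients, b = 0.5, no baseline covariates:

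| Assumed truth | B-FIT-only test significant | Both-arm test significant |
|---|---|---|
| Assignment does not shift M; a 0.8 SD arm effect bypasses M; X–M correlation 0.5 within B-FIT | 68% | 6% |
| Assignment shifts M by 0.8 SD and the whole arm effect runs through M; X unrelated to M within B-FIT | 6% | 75% |

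These rates use 1,000 trials and 500 resamples. With 3,000 trials and 1,000 resamples, the first row gives 65% and 5% at a correlation of 0.5, 26% and 6% at 0.25, and 5% and 5% at zero. The rate thus depends heavily on the assumed correlation. The table shows only that the two tests answer different questions; it does not predict this trial's error rate.

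**Precision of a both-arm model.** On the same assumptions (b = 0.5, 34 versus 17), the both-arm test is significant in about 14% of trials if assignment shifts the mediator by 0.25 SD, 39% at 0.5 SD and 73–75% at 0.8 SD.

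**The case against.** The strongest reply is that the restriction follows from the question in the objectives. Ingredient ratings are scored from recorded B-FIT sessions, so TAU patients have none. For a preliminary study of active ingredients, a B-FIT-only model is coherent. This stands, and it is why the six models should be kept. It does not support the broader question that opens Aim 2c in the statistical section.

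Second, Aim 2a already supplies a randomized comparison for TAU adherence. If B-FIT failed to move adherence, that test could show it. This also stands, but Aim 2a does not link adherence to drinking and does not compare the arms on commitment or perceived family support.

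Third, adjusting for baseline mediators removes some confounding by stable traits. That is true. It does not address engagement that emerges during treatment, and it cannot restore the missing contrast.

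Fourth, the added model has limits of its own: low precision, and a mediator-to-outcome path that is still observational. Both must be stated with the result.

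A reader might go further and infer that the plan discards its randomized information, that the B-FIT-only models are wrong, or that Table 1 shows every mediator to be available in both arms. The documents support none of these. Aims 2a and 2d use both arms, and the within-arm models suit the objective. The columns of Table 1 cannot be read reliably in the text available. Within-treatment forms follow sessions, apparently B-FIT sessions, so mediators recorded during treatment may not exist in TAU.

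**Conclusion.** The point holds as a mismatch between the question and the analysis population. As planned, Aim 2c can report exploratory, non-randomized associations within the B-FIT arm. It cannot say why B-FIT differed from TAU, and no other part of the plan supplies a mediation test across arms. This follows from the model structure and needs no assumed effect size. The 33% of followed patients left out applies to Aim 2c only. How often a misleading result would occur cannot be derived from the documents; the simulated rates depend on the assumed effects.

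The fault is one of interpretation plus one missing model. It changes what the trial may conclude about mechanism and leaves the Aim 2a comparisons untouched.

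**What to change.** 1. Keep the six B-FIT-only models. State in Aim 2c that they are exploratory within-arm associations between ingredient delivery, mediator and outcome, and that they will not be reported as the reason for any B-FIT versus TAU difference.
2. Add one mediation model in all randomized patients, from assignment to TAU adherence to PDA, adjusted for the covariates already named for adherence in Aim 2a. If the TSR or Form-90 gives session dates, use earlier adherence against later monthly PDA. The plan defines adherence only as a total to month 4, so it should say whether dates are available. If they are not, report that mediator and outcome overlap in time.
3. Extend the model to commitment and perceived family support only if the sponsor confirms that patients in both arms complete these scales at baseline and follow-up.
4. Report the indirect effect as an estimate with its bootstrap interval, and state the limits: about 34 versus 17 patients, a mediator-to-outcome path that is not randomized, and month-4 mediators concurrent with the outcome. The average residential stay is 18–21 days, so early adherence may largely reflect inpatient attendance.

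The cost is a change of wording, one extra model and a check of what TAU patients complete. Adherence needs no new data collection if dates are held. The added model does not cover shared time or communication, for which only the within-arm reading remains.
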